**Table 3. Schedule of invitation, consent and implementation of WP2 patient/carer discussion group meeting**

	Pre-Consent	Informed Consent	Post-Consent
Weeks	0	8 	8
VPLG member given WP2 PIS/ICF (including invitation letter) by recruiter (VPLG Coordinator or suitable site delegate) at a routine VPLG meeting	X		
Participant completes and returns reply slip confirming if they agree to be contacted about attending a discussion group meeting 	X		
Recruiter liaises with member and ADVANCE Trial Manager to arrange attendance at discussion group meeting	X		
VPLG Co-Ordinator takes Informed consent prior to discussion 		X	
Discussion group meeting (duration approximately 1.5 hours)			X
Withdrawal as applicable 			X

 Taken from the HRA CTIMP protocol template (2016).

 Participants that decline to take part must not be contacted further for the purposes of this trial.

 Participant must be given a minimum of 24 hours after receipt of the PIS/ICF before informed consent is taken.

 Participant, or researcher/clinician must complete a copy of the ADVANCE Withdrawal of Consent Form and email to [[contact]](mailto:[contact]) immediately.

 The discussion group meeting will be conducted as soon as possible after the VPLG member has agreed to further contact about the meeting, and where feasible within 8 weeks.

### 12.3 WP3: Healthcare worker discussion group meeting

Approximately 15 healthcare workers will be invited to participate in WP3 and given a copy of the ADVANCE WP3 PIS/ICF [27] by a member of the local site trial team assigned the role of recruiting participants on the local site staff delegation log as specified in Section 9. The potential participant will be asked to return the reply slip to the recruiter by email or hand. Potential participants who decline to take part must not be contacted further by the recruiter for the purposes of recruitment. The local trial team will liaise with the potential participant and the ADVANCE Trial Manager to arrange attendance at a discussion group meeting to be held at VCC or a suitable alternative location

at the University of Wales Hospital Heath Site or Cardiff University at a specified future date and time, or using a virtual video conferencing platform if required.

**Table 4. Schedule of invitation, consent and implementation of WP3 healthcare worker discussion group interview**

	Pre-Consent	Informed Consent	Post-Consent
Weeks	0	8 	8
Healthcare worker given WP3 PIS/ICF (including invitation letter) by recruiter	X		
Healthcare worker completes and returns reply slip confirming if they agree to be contacted about the focus group meeting 	X		
Recruiter liaises with member and ADVANCE Trial Manager to arrange attendance at discussion group meeting	X		
Trial Manager takes Informed consent prior to discussion 		X	
Discussion group meeting (duration approximately 1.5 hours)			X
Withdrawal as applicable 			X

 Taken from the HRA CTIMP protocol template (2016).

 Participants that decline to take part must not be contacted further for the purposes of this trial.

 Participant must be given a minimum of 24 hours after receipt of the PIS/ICF before informed consent is taken.

 Participant or Trial Manager must complete a copy of the ADVANCE Withdrawal of Consent Form and email to [[contact]](mailto:[contact]) immediately.

 The discussion group meeting will be conducted as soon as possible after the healthcare worker has agreed to further contact about the meeting, and where feasible within 8 weeks.

## 12.4 Implementation of the WP2 Patient/Carer and WP3 Healthcare worker discussion group meetings

The potential participant will be asked to bring the relevant WP2 or WP3 PIS/ICF [26, 27] with them to the meeting, and to sign the ICF upon on arrival at the meeting before the discussion starts or emailed to the organiser ahead a virtual meeting and verbally consented prior to the start of a virtual meeting, as specified in Section 9. The meeting will last about 60-90 minutes and will be arranged at a date and time convenient to those taking part. The interview will be held at VCC in Cardiff where feasible, or at either the University Hospital of Wales, Heath Park Site or Cardiff University campus, or using a virtual video conferencing platform if required. About 10-15 participants will take part in each meeting.

The WP2 patient/carers meeting will be led by one or more VPLG Coordinator(s) who is employed at the participating site and has experience of discussing cancer research with patients and their carers in the group setting.

The WP3 healthcare worker meeting will be led by a member of the CTR ADVANCE team with a background in cancer and/or qualitative research.

Representative(s) from the ADVANCE trial team will be present as observers. The total number of people present at each meeting will be no more than 20.

After consent and prior to the discussion, the OLO System will be digitally demonstrated to explain how it can be used to detect a low white blood cell count. The meeting leader will then ask the participants their views about potential use of the system to manage cancer patients who have suspected neutropenic sepsis whilst receiving chemotherapy following a list of question topics that has been approved by REC. The interviewer and/or observers will make handwritten notes to record the discussion. The participants will be able to ask the leader to pause the meeting at any time. At the end of the meeting, the leader will check once again that each participant continues to provide consent for their conversation to be included in the trial.

WP2 participants who are cancer patients will be permitted to leave the interview early if they are thought to be fatigued or become unwell.

WP2 and WP3 participants will not be paid for participating in this study and the study may not benefit them personally. Participants will have to arrange their own transport to the meeting, if applicable, and will not be paid travel expenses.

## **12.5 Development of WP1 Participant Acceptability Survey**

The WP1 device evaluation will take place after WP2. The patient/carer discussion group meeting will be used to inform the design of a survey to record the experience of cancer patients recruited to WP1 Cohort 3.

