Eligible participants will be asked to consent to this part of the study upon presentation at the hospital. We will test their blood using the routine laboratory method and the OLO System. We will use the

data to determine the accuracy and safety of the OLO System compared to the standard laboratory test.

2) The acceptability of using the OLO System to patients and their carers. We will conduct a discussion group meeting with cancer patients and their carers to identify appropriate acceptability issues, concerns, topics and questions. Attendees will be recruited via the Velindre Patient Liaison Group (VPLG) and Velindre Patient Experience Manager or a suitable delegate at VCC, Velindre University NHS Trust. Potential attendees will be given a participant information sheet (PIS) providing further information about the meeting and asked to provide written consent via an Informed Consent Form (ICF) and/or verbal consent prior to their participation. The meeting will be held in Cardiff or remotely online. The discussion will be recorded via hand-written notes documenting participants' responses. Notes will be summarised in digital format and used to design a participant survey that will be submitted for Research Ethics Committee (REC) approval. Patients recruited in part 1) above will then be asked to consent to complete the ethically approved survey. Their responses will be analysed to find out if replacing the standard laboratory test with the OLO (System is acceptable to patients and their carers.

3) The acceptability of using the OLO System to healthcare professionals. We will conduct a second discussion group meeting with health care professionals (for example, nurses, doctors, senior house officers, phlebotomists, etc.) who have been involved in the testing of the OLO System in 1) above. Potential attendees will be provided with a PIS providing further information about the meeting and asked to provide written consent via an Informed Consent Form (ICF) and/or verbal consent prior to their participation. The discussion will be recorded via hand-written notes and summarised in digital format. Participants' responses will be analysed to find out if replacing the standard laboratory test with the OLO System is acceptable to healthcare workers. Topic areas may include ease of use, accuracy, safety, impact on current patient management pathways and procedures, etc.

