### **5.1 Objectives**

To clinically evaluate the investigational device (OLO (System) versus the comparator standard laboratory device for the management of chemotherapy-related suspected neutropenic sepsis and pre-chemotherapy borderline neutropenia.

The secondary objectives of the study are:

1. To assess the feasibility of recruiting patients and use of the OLO (System);
2. To assess the safety of the OLO (Sight Diagnostics) System in association with the UKONS Oncology/Heamatology 24 hour guidance and triage screening tool (Appendix 1) for patients who telephone for medical advice with suspected neutropenia and sepsis, to maximize both patient safety and independence;
3. To assess patient and staff acceptability for the investigative device;
4. To assess costs, including issues around hospital care/treatment and admissions.
5. To assess which chemotherapy regimens are most likely to be associated with neutropenic sepsis and what current treatment management is;
6. Through communication with key stakeholders and Welsh Government, explore the framework required to adequately inform the potential integration of the investigational device and triage questions into routine practice, within Wales and beyond;
7. To design a larger UK-wide trial, in collaboration with patient representatives, to formally assess the investigational device for routine use within the NHS.

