### **6.2 Work Package 2 (WP2): Patient/carer acceptability**

This qualitative WP2 will assess the key components that would make this feasibility trial and any future larger trial acceptable to patients. WP2 will be led by the VPLG Coordinator or suitable site staff delegate, with support from the Qualitative Researcher, CI and Trial Manager. This WP will focus on a discussion group looking at acceptability to patients and carers for use of the OLO (Sight Diagnostics) system to manage patients with chemotherapy-related suspected neutropenic sepsis and will be implemented prior to WP1.

**Figure 6.** Routine patient management pathway for patients presenting at pre-chemotherapy or paclociclib assessment with borderline neutropenia

Up to 15 members of the VPLG will be invited to participate in a discussion group meeting. Up to 10-15 patients and/or carers will take part. The interview will be held at the participating site, VCC or suitable alternative at the Cardiff. Participant consent will be collected remotely prior to the interview by the VPLG Coordinator or suitable site staff delegate. The interview will include a digital visual demonstration of the OLO System, including the testing equipment and blood sample collection consumables, implemented by the interviewer. The interviewer will use a list of key discussion topics to explore the views of the group about use of the OLO System to manage chemotherapy-related neutropenic sepsis. Key discussion topics will include but not be limited to:

- Views about the current patient management pathway (for example telephone triage, hospitalisation, administration of antibiotics prior to test results, etc.).
- Confidence in the OLO technology as an alternative to the standard test.
- Perceived benefits and disadvantages of the OLO technology.
- Views about the positioning of the OLO technology (for example, community, primary, secondary or tertiary care, Tenovus mobile unit).
- Views about the self-operation of a modified version of the OLO System or similar alternative device.
- Exclusion criteria for future large-scale study (if appropriate) based upon ability to use the equipment effectively, including dexterity and cognitive ability.
- Participant acceptance survey topics.

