The discussion group meeting will be manually recorded in anonymised written note format and summarised in anonymised digital format (for example Microsoft Word). The summary will be used to assess the acceptability of the device and application to patients and their carers. It will also be used to develop a participant acceptability survey that, following approval by REC, will be used as a patient evaluation tool to assess acceptability of the equipment. This patient evaluation tool will be completed by participants of WP1, the device cohort comparator study, Cohorts 1-3.

This work will assist in the design of a larger trial and will involve liaison with:

- VPLG.
- Wales Cancer Research Centre (WCRC).
- Tenovus.
- Healthcare workers.

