##### **Cohort 3: Patients who have not had blood assessed by the OLO device but have received therapy that can cause a low white blood cell count.**

- 1) 18 years old or over
- 2) Patients receiving or who have received cytotoxic chemotherapy or radiotherapy

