Study samples must not be removed from routine venous samples until the sample has stood for **at least 20 minutes**. If this process will prevent the routine sample from reaching the routine laboratory within the required local and/or national permitted timeframe a finger prick sample must be taken instead.

Samples tested in the OLO (Sight Diagnostics) analyser will be destroyed following local hospital procedures immediately following conduct of the study test. The samples will not be stored for future research.

The participant and their treating hospital consultant will only be told the results from their standard care tests. The result from the study tests will **not** be used to manage the participant.

If the standard care test(s) show that the participant has neutropenic sepsis their treating hospital consultant will decide what treatment they need (for example whether or not they need to continue taking antibiotics, stay in hospital, or can be discharged) in discussion with the participant and following local standard procedure.

### **12.1.3 .....ADVANCE Qualitative Acceptability Survey**

Prior to discharge from the hospital, Cohort 3 participants will be given a paper copy of the ADVANCE Survey [33] to complete about their views around the study and our intended use of the new equipment

The healthcare professional will ask the patient to complete the survey before they leave the hospital following their discharge. The survey will take about 30 minutes for the participant to complete. Completed surveys will be handed to the local PI.

**12.1.4 ..... Baseline toxicity data**

Baseline toxicity data will be collected after consent and prior to collection and analysis of study blood samples. SAEs must be reported following the timeframes and procedures specified in Section 13.

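### The protocol contradicts itself on who completes the acceptability survey; if Section 12 and Table 2 are followed, none of the 72 participants planned for OLO testing is surveyed

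*Protocol*

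**What the plan says.** Secondary objective 3 (Section 5.1) is "To assess patient and staff acceptability for the investigative device".

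**Text that gives the survey to Cohort 3**
- Section 12.1.3: "Cohort 3 participants will be given a paper copy of the ADVANCE Survey".
- Section 12.5: a "survey to record the experience of cancer patients recruited to WP1 Cohort 3".
- Section 6.1.3: an anonymous survey for Cohort 3, n=24.
- Table 2: the rows for giving out and returning the survey sit under the block for Cohort 3 alone.
- Table 8: participant acceptability appears as a source-data item only under Cohort 3.

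Section 8.1.1 heads Cohort 3 as "Patients who have not had blood assessed by the OLO device but have received therapy that can cause a low white blood cell count".

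**Text that gives the survey to tested patients, or to everyone**
- Section 6.2: "This patient evaluation tool will be completed by participants of WP1, the device cohort comparator study, Cohorts 1-3".
- Section 3.2: "Patients recruited in part 1) above will then be asked to consent to complete the ethically approved survey". Part 1) is the OLO comparison, described there as two cohorts: acute admissions and pre-chemotherapy checks.
- Section 14.1.1, Cohort 1: an 80% survey return, 38 patients, 95% CI 65.7% to 88.3%.
- Section 5.3: the survey-return outcome has all recruited participants as its denominator.

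**The other patient source.** The WP2 discussion group is held before WP1. Of that meeting Section 6.2 says: "The interview will include a digital visual demonstration of the OLO System". The patient-acceptability outcome in Section 5.3 and the patient criterion in Table 7 both draw on this group.

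**The concern.** The sections that site staff would work from (12.1.3, 12.5, the Table 2 schedule and the Table 8 source-data list) all point to Cohort 3. The sections that state the survey's purpose, precision and outcome definition point to Cohorts 1 and 2, or to all participants. A site cannot satisfy both sets.

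The choice decides what the survey measures. Cohort 3 patients can say how they regard a test described to them. Only patients in Cohorts 1 and 2 can say how they found the sampling, or a second sample after a test error, some of them while acutely unwell. Section 4.2.2 says that patient acceptance still has to be assessed, including in frailer and less dextrous people. If the survey stays with Cohort 3, every patient view taken into the design of the larger trial comes from people who have not had the test, and the missing views are hard to recover once tested patients have left hospital.

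**Working it through.** **1. Inputs**
- Recruitment targets: Cohort 1, 48; Cohort 2, 24; total in the device comparison, 72 (Synopsis and Section 9.3.1).
- Cohort 3: 24 approached, at least 19 completed surveys (Section 9.3.1).
- Assumed survey return: 80% (Section 14.1.1 for Cohorts 1 and 3; Table 7 as a criterion).

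**2. Reproducing the protocol's figures**

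The Wilson score interval is
(p + z²/2n ± z·√[p(1−p)/n + z²/4n²]) / (1 + z²/n), with z = 1.96.

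For 38/48, p = 0.7917 and z²/n = 3.8416/48 = 0.0800:
- centre = (0.7917 + 0.0400)/1.0800 = 0.7701
- half-width = 1.96 × √(0.003436 + 0.000417)/1.0800 = 0.1126
- limits 65.7% to 88.3%, as stated.

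| Proportion | Recomputed (Wilson) | Stated in 14.1.1 |
|---|---|---|
| 38/48, Cohort 1 survey | 65.7% to 88.3% | 65.7% to 88.3% |
| 24/48, Cohort 1 widest | 36.4% to 63.6% | 36.4% to 63.6% |
| 19/24, Cohort 3 survey | 59.5% to 90.8% | 59.5% to 90.8% |
| 12/24, Cohort 3 widest | 31.4% to 68.6% | 31.4% to 68.6% |

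Exact (Clopper-Pearson) and Wald intervals do not match. For 38/48 they give 65.0% to 89.5% and 67.7% to 90.7%. The arithmetic in Section 14.1.1 is therefore sound. The Cohort 1 line is a worked calculation that needs 48 Cohort 1 patients to be eligible for the survey.

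**3. If Section 12 and Table 2 are followed**
- Tested participants surveyed: 0 of 48 + 24 = 72.
- Cohort 1 surveys: 0, so the 38/48 interval has no data behind it.
- Return proportion as defined in Section 5.3: all recruited = 48 + 24 + 24 = 96. If every Cohort 3 patient returns a survey, 24/96 = 25%. With the planned 19, 19/96 = 19.8%. If a Cohort 3 patient counts as recruited only on returning a survey, 19/(72 + 19) = 20.9%, and the ceiling is still 24/(72 + 24) = 25%.
- Table 7 survey criterion: its denominator is those given the survey, so 19/24 = 79% can be calculated. Table 7 and Section 5.3 thus use different denominators for the survey return.

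**4. If Section 6.2 is followed (Cohorts 1-3)**
- All cohorts: 80% of 96 = 76.8, about 77/96, Wilson 71.1% to 86.9%.
- Tested patients: 80% of 72 = 57.6, about 58/72, Wilson 70.0% to 88.0%. Rounding down within each cohort gives 38 + 19 = 57, and 57/72 has Wilson limits 68.4% to 86.9%.
- The 80% return in Cohort 2 is an assumption; Section 14.1.1 gives no survey figure for that cohort.

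**The case against.** **The stronger reading.** A reader might infer that the survey is fixed as Cohort 3 only, that no tested patient will ever rate the test, and that the patient-acceptability objective therefore cannot be answered. The documents do not support this.
- Cohort 3 only is one side of an unreconciled contradiction. Sections 3.2, 5.3, 6.2 and 14.1.1 say otherwise.
- The named patient-acceptability outcome and its Table 7 criterion use the WP2 discussion group. The survey is not listed under acceptability in Section 5.3; its return rate is a feasibility outcome. Perceived acceptability can be described on either reading.
- The survey-fidelity criterion is a return rate among those given the survey and does not depend on whether they were tested.

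**Limits on what tested patients could add.** They are not told their OLO result (Section 12.1.2), so they could not rate confidence in it from experience. A venous aliquot may replace the finger prick, so the number with a distinct sampling experience is unknown and may be below 72. Re-takes, flags and error codes are recorded as outcomes, and finger-prick site events are reported. What would be missing is the patients' own account of discomfort and burden.

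**In favour of Cohort 3.** Section 12.1.3 describes the survey as covering views on the study and the intended use of the equipment, which untested patients at risk can give. Section 12.5 does not say experience of the device. The amendment history shows that Cohort 3 was added deliberately to broaden the survey, and the Cohort 1 survey text may predate it.

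All of this stands. It narrows the point but does not remove it: the conflicting sentences are all in the current text, and the amendment history does not say that Cohorts 1 and 2 are no longer surveyed.

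**Conclusion.** The point holds as an inconsistency that changes what is measured. Sections 6.1.3, 12.1.3 and 12.5 and Tables 2 and 8 cannot be reconciled with Sections 3.2, 5.3, 6.2 and 14.1.1. If the procedural text is followed, 0 of 72 planned tested participants are surveyed, the stated Cohort 1 precision (38/48) cannot be delivered, and the Section 5.3 return proportion is capped at 25%. Patient acceptability can then be reported only as perceived by Cohort 3 and the WP2 demonstration group. Experienced acceptability cannot be reported.

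This rests on the recruitment targets in the Synopsis and Section 9.3.1, and on counting Cohort 3 among all recruited participants for Section 5.3. If that phrase means Cohorts 1 and 2 only, the return proportion would be 0/72. The survey itself and the qualitative analysis plan were not available.

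**What to change.** State one survey population and carry it through Sections 3.2, 5.3, 6.1.3, 6.2, 12.1.3, 12.5 and 14.1.1 and Tables 2, 7 and 8.

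**Preferred: make Section 6.2 operative.**
- Offer the survey to Cohorts 1 and 2 after the OLO test, alongside Cohort 3.
- Settle the consent route first. Implied consent, with no withdrawal after submission, is described only for Cohort 3. Cohorts 1 and 2 give written consent, are registered under trial numbers and may withdraw; Section 3.2 says device-study patients are asked to consent to the survey, and Section 6.2 gives no consent mode.
- Obtain ethics approval for the changed procedure.
- Record sample type on the survey (finger prick, venous aliquot, not tested) and report tested and untested respondents separately.

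**If Cohorts 1 and 2 are closed or will not be surveyed.**
- Delete the Cohort 1 survey precision figure from Section 14.1.1.
- Make the Section 5.3 denominator those given the survey, as in Table 7.
- Correct Sections 3.2 and 6.2.
- Restate the patient part of objective 3 as perceived (anticipated) acceptability in patients not tested with OLO.

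**Cost.** The second route costs wording and an amendment. The first adds ethics approval of the changed survey procedure and about 30 minutes per tested patient, the completion time given in Section 12.1.3.
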